# 1.0 Objectives

1.1 Aim 1 (Phase 1): To conduct 5 focus groups for the development of two theory-based, video podcast-delivered, HIV prevention interventions for self-identified heterosexual African American males and females. Aim 2 (Phase 2): To evaluate the effectiveness of the two theory-based, video podcast-delivered, HIV prevention interventions for self-identified heterosexual African American males and females.

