### 3.0 Inclusion and Exclusion Criteria

- Phase 1 & 2: Individuals eligible to participate will: (1) self-identify as African American; (2) reside in a low SES predominantly African American super neighborhood; (3) speak and read English; (4) be 18 years old or older; and (5) not previously diagnosed with HIV. The screening questionnaire will assess these eligibility criteria (attached in the smartforms).
- 3.2 Phase 1 & 2: Potential participants will call dedicated university phoneline or email study team email account. Flyers will be distributed at African American-based community events; contact information will be displayed on the flyers.
- 3.3 The following groups will be excluded. The research may possibly involve economically and/or disadvantaged persons.
  - Adults unable to consent
  - Individuals who are not yet adults (infants, children, teenagers)
  - Pregnant women
  - Prisoners
  - Students for whom you have direct access to/influence on grades

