### 7.0 Multisite -N/A

# **8.0** Study Timelines

- Phase 1: The total duration of an individual's participation in the study is no more than 1.5 hours. The number of study visits is 1 per participant. No follow-up is included in the study. It is anticipated that it will take approximately 10 minutes to consent each participant. The estimated date of completion for this phase of the study (focus group phase) and primary analyses is March 30, 2022.
- Phase 2: The total composite time duration of an individual's participation in the study is estimated to be about 60 minutes. The number of study visits is 3 per participant. All study "visits" are in the form of online survey and video viewing. The first study visit will consist of consenting via cover letter and pre-test. The second study visit will consist of a 1 month-follow-up survey video podcast viewing. The third study visit will consist of a short follow-up survey 3 months following post-test completion. It is anticipated that it will

take approximately 5 minutes to recruit/enroll each participant; 15 minutes to complete the pre-test; 20 minutes to watch draft podcast video; 15 minutes to complete the posttest; and 5 minutes to complete the 3-month follow-up. The estimated date of completion for this phase of the study and primary analyses is August 30, 2023.

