# 9.0 Study Endpoints

- 9.1 The primary study endpoint for the proposed study shall be 3 months following the last participant's post-test in Phase 2 and been analyzed.
- 9.2 There are no primary or secondary safety endpoints to be described.
- 9.3 "There are no safety endpoints given that there are no safety risks associated with the study."

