### 10.0 Procedures Involved

### 10.1 Study Design:

Phase 1: The study design is focus group methodology, a qualitative research design in which participants are guided through a freeform discussion of a particular issue. The results of will reflect perceptions about HIV that are validated directly from the participants themselves. Five focus groups will be conducted.

Phase 2: The study design is quantitative repeated measures methodology. Participant data will be de-identified and used aggregately in repeated measures analyses (N=128).

10.2 Phase 1: Participants will be introduced to the study and given written informed consent, with an opportunity to ask any study related questions. Participants will be notified that they will be digitally audio recorded throughout the duration of the focus group session. The moderator will introduce herself and instruct the participants to identify themselves with a pseudonym of their choice, and not to use their real names. The moderator will begin by asking the first question. Once discussion has begun, the moderator will guide the focus group discussion with a series of questions using the focus group script. [The focus group script of questions can be found in the SmartForms. The moderator will take notes throughout the focus group sessions that will provide context, if needed, throughout the discussion. The moderator will carefully watch the time, making sure that all questions are asked during discussion within the 1.5-hour time allotted for participation. Participants will be thanked for their participation, provided light refreshments, and will be given a Target, Amazon, or Wal-mart gift card of \$45 for participation.

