Phase 2: Participants will email or call a dedicated study email/phone line, where research assistants will screen them, answer any questions they may have, and get them formally enrolled, if applicable. Participants will be given a unique ID number. Participants will be emailed a secure unique link to the pre-test survey (which will include cover letter consent information – See Section 22.1). Participants will complete the pre-test measure. One month after pre-test survey completion, participants will be emailed a secure unique line to the post-test survey in which they will view the podcast video and complete the post-test measures. Participants will be emailed a secure unique link 3 months later to complete a brief behavioral outcome questionnaire. The research team will be knowledgeable about the podcasting software in order to assist participants in trouble-shooting, if necessary. Dark Light Studios will also provide consulting throughout the entire research process, if needed. Upon pre-test completion, participants will be emailed (or pick up in person) a \$20 Walmart, Target, or Amazon gift card; \$80 Walmart, Target, or Amazon gift card upon post-test completion; and \$25 Walmart, Target, or Amazon gift card upon 3 month follow-up completion; for an opportunity to receive \$125 for complete participation. For participants who do not have email addresses, research assistants will assist them in obtaining one, within the recruitment procedures, if desired; alternately, participants will be able to schedule a time to meet at one of the community centers in order to complete pre- and post-test surveys in person, and/or to pick up gift card, if needed.

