# [Eligibility Screening Script and Focus Group Script are attached in SmartForms]

Phase 2 – Survey Data: Demographics will include age, biological sex, education, and income. Based upon the behavioral outcomes we expect participants to adopt from the HIV prevention podcasts, we will inquire (pre, 1 mo post, & 3mo): (1) frequency of penetrative sexual intercourse acts in the past month, (2) unprotected penetrative sexual intercourse in the past month, (3) number of sexual partners in

the past month, (4) PhenXToolkit Self-reported HIV Results, and (5) condom use during the last act of penetrative sexual intercourse. Based on the knowledge and psychosocial cognitions we expect to influence, measures (pre & post) will consist of (1) Motivations to use condoms scale, (2) HIV knowledge, (3) attitudes toward condom use, (4) condom use self-efficacy, and (5) condom use communication, (6) perceived social and subjective norms, (7) feedback concerning HIV prevention video content and presentation (1 mo post only), and (8) Marlowe-Crowne social desirability scale(1 mo post only). [A copy of the survey measures is attached in the SmartForm section]

10.4 1 month and 3 month follow-up data will be collected from Phase 2 participants. No follow-up data will be collected form Phase 1 participants.

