## 25.0 Data Management

- 25.1 Phase 1: Data Analysis will include transcribing the focus group data, examining all the transcriptions aggregately and analyzing the qualitative data for common themes, as thematic analysis will constitute the analysis procedure.
  - Phase 2: Data analysis will include aggregating the data, eliminating any identifiers, and performing repeated measures t-tests on the study variables of interest.
- 25.2 Phase 1: Electronic data (audio files and transcripts) will be secured and encrypted on my on-campus university computer in my office. Consent forms, will be stored in separate folders in a locked file cabinet.
  - Phase 2: Electronic data will be secured and encrypted on my on-campus university computer in my office. Study key code spreadsheet (linking participant ID number with email address) will be encrypted and stored securely on my office computer.
- 25.3 Data will be stored for seven years
- 25.4 Only the PI (researcher) and approved student research team members will have access to the raw data.
- 25.5 The PI (researcher) will be responsible for receipt of the data (Both Phases).
- 25.6 Phase 1: One approved student research team member will have access to the audio files and will be responsible for all audio transcription.Transcription will take place only on the PI's university-issued laptop within the researchers' office during student researcher's work hours. Audio transcription files will be password protected on the UH secure server.

Phase 2: Approved student researchers will have access to the de-identified data. All data analyses will take place only on the PI's university-issued laptop within the researchers' office during student researcher work hours.

25.7 Data will not be banked for future use.

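### Phase 2 names no primary outcome or contrast, and four of its 11 possible pre-versus-post tests (five with the HIV result) concern time before the video is seen

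*Combined protocol and SAP*

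**What the plan says.** - **Aim.** Section 1.1, Aim 2: "To evaluate the effectiveness of the two theory-based, video podcast-delivered, HIV prevention interventions". No outcome is named.
- **Primary endpoint.** Section 9.1: "The primary study endpoint for the proposed study shall be 3 months following the last" participant's post-test. This is a point in time. It gives no variable, summary measure or contrast.
- **Analysis.** Section 25.1: "Data analysis will include aggregating the data, eliminating any identifiers, and performing repeated measures t-tests on the study variables of interest". Section 10.1 adds only that the data will be "used aggregately in repeated measures analyses (N=128").
- **Measures.** Section 10.3 lists five items under behavioural outcomes, on which "we will inquire (pre, 1 mo post, & 3mo"). Three have a past-month window (frequency of intercourse, unprotected intercourse, number of partners). The other two are a self-reported HIV result and condom use at the last act. It also lists six knowledge or psychosocial measures taken at pre-test and post-test, and two taken at post-test only.
- **Timing of the video.** Section 8.0: "The second study visit will consist of a 1 month-follow-up survey video podcast viewing". Section 10.2: one month after the pre-test, participants are sent a link to the "post-test survey in which they will view the podcast video and complete the post-test measures". A behavioural questionnaire follows 3 months later.

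**The concern.** Aim 2 is an effectiveness claim, and the plan does not say which result would support it. Two separate problems follow.

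The first is selection. With many measures, two follow-up times and no ranking, a significant result can be picked out after the data are seen.

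The second is timing, and it does not depend on how many tests are run. If the video is first seen during the post-test session, behaviour reported in that session happened before viewing. A change from pre-test to post-test on those items may be real, for instance a reaction to being surveyed or drift over a month, but it cannot be caused by the video. Section 25.1 does not rule out testing it and reporting it as effectiveness.

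**Working it through.** **1. Is anything primary?** Sections 1.1, 9.1, 10.1, 10.3 and 25.1 were read together. 10.3 identifies the measures and their waves. None of the five sections ranks an outcome, names a pair of time points, or gives an alpha or a multiplicity rule. The plan has no stated error rate to reproduce, so 0.05 two-sided per test is assumed below.

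**2. How many tests (10.3)?**
- Pre versus post: 5 behavioural-group items + 6 scales = 11.
- Adding pre versus 3 months for the five items: 11 + 5 = 16.
- Adding post versus 3 months as well: 16 + 5 = 21.
- Without the HIV result: 10 and 14 in place of 11 and 16.
- Narrowest reading, the four behaviours at pre-test versus 3 months: 4.

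**3. Which pre-versus-post tests can reflect the video?** Sections 8.0 and 10.2 both put the viewing in the post-test session.
- Three items look back over the past month, which is before viewing.
- The last act of intercourse also precedes the session.
- The HIV result is a test result and not a behaviour, but it too refers to earlier time.

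So 4 of 11 tests, or 5 of 11 with the HIV result, cannot show an effect, whichever part of the survey comes first. The six scales can change on viewing. The 3-month questionnaire is the only behavioural measurement after viewing.

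**4. Chance of at least one false positive.** For k independent tests this is 1 − 0.95^k; for k = 11, 1 − 0.5688 = 0.431. With a common correlation ρ between test statistics it is 1 − E[(Φ((1.96 − √ρ·Z)/√(1−ρ)) − Φ((−1.96 − √ρ·Z)/√(1−ρ)))^k], Z standard normal, by quadrature. The correlations are assumptions.

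| Tests | ρ = 0 | ρ = 0.3 | ρ = 0.5 |
|---|---|---|---|
| 4 (narrowest) | 19% | 17% | 16% |
| 10 (pre vs post, no HIV result) | 40% | 35% | 29% |
| 11 (pre vs post) | 43% | 37% | 30% |
| 14 (both follow-ups, no HIV result) | 51% | 44% | 35% |
| 16 (both follow-ups) | 56% | 48% | 37% |
| 21 (all pairs of waves) | 66% | 55% | 43% |

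**5. What the repair can detect (80% power).**
- *Yes/no outcome, McNemar mid-p.* If a share D of participants switch answers and the net change is Δ, a switch is in the favourable direction with probability (D + Δ)/(2D). The exact mid-p test is averaged over a Binomial(n, D) number of switchers. D = 20% to 40% and a 20% loss by 3 months are assumptions (0.8 × 128 ≈ 102; 0.8 × 64 ≈ 51).

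| Analysis | Pairs | Detectable Δ, D = 20% / 30% / 40% (points) |
|---|---|---|
| Pooled, 0.05 | 128 | 10.8 / 13.3 / 15.4 |
| Pooled, 0.05 | 102 | 12.0 / 14.9 / 17.2 |
| Per sex, 0.025 | 64 | 15.8 / 20.1 / 23.4 |
| Per sex, 0.025 | 51 | 17.4 / 22.0 / 26.1 |

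- *Scale, paired t-test* (noncentrality d√n, d in SD of the change score). At 0.05, d = 0.25 with 128 pairs and 0.28 with 102. At Holm's first step over 10 outcomes (0.05/10 = 0.005), d = 0.33 and 0.37.

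**The case against.** **The variables are not unnamed.** This stands. The variables in 25.1 naturally mean the list in 10.3, so a reader who infers that the outcomes are unspecified goes too far. What is missing is a ranking and a contrast.

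**Section 9.1 may point to the 3-month wave, where only the behavioural-group items are collected.** This is possible but weak, because 9.1 reads like a completion date. Even so, four behaviours remain unranked, which is the 16% to 19% case.

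**The 1-month label in 10.3 could mean one month after viewing.** Read alone, it could. Sections 8.0 and 10.2 both place viewing in the post-test session and outweigh it, but the texts need to be reconciled. The survey forms are attachments that were not available, so item wording and order could not be checked.

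**The HIV result may never be t-tested**, since entry requires people "not previously diagnosed with HIV". That is fair. The count then becomes 4 of 10, and the timing problem remains.

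**Stronger readings a reader might infer.** One is that no pre-versus-post test is informative; the six scales contradict this, because 10.2 describes viewing the video and then completing the post-test measures. Another is that the investigators intend to claim success on any single significant test. The documents state no success rule. They leave this open, which is not the same as planning it.

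**Conclusion.** The concern holds and should be corrected before Phase 2 data are analysed. The plan designates no primary outcome or contrast, and it permits four behavioural comparisons (five with the HIV result) that cannot bear on the video's effect.

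The timing finding rests on 8.0 and 10.2 as written and needs no numerical assumption. The false-positive range, from 16% on the narrowest reading at ρ = 0.5 to 56% for 16 independent tests, rests on an assumed 0.05 per test and assumed correlations; testing every pair of waves would raise it further.

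These percentages measure chance error only. They do not measure the risk of crediting the video with a real change that came before it. Nor would a single primary test at 5% bring the risk of a false effectiveness claim down to 5%: Phase 2 has no control group, and a pre-test to 3-month comparison spans about four months in which behaviour may change for other reasons.

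**What to change.** 1. **Section 25.1, contrast.** Test behavioural outcomes as pre-test versus 3-month follow-up. Report behaviour from the post-test survey as a second pre-viewing baseline, not as evidence of effect. Reconcile the 1-month label in 10.3 with 8.0 and 10.2.
2. **Section 9.1, primary outcome.** Name one outcome and contrast from the measures already collected, at the investigator's choice: a behaviour at pre-test versus 3 months, or a scale at pre-test versus post-test. State whether it is tested pooled (two-sided 0.05) or for each sex and video (0.025 each). Aim 2 concerns two interventions, and a pooled test does not evaluate each of them.
3. **Section 25.1, method.** Use a paired method that suits the outcome type, for example McNemar for yes/no items and the planned paired t-test for scales. If condom use at the last act is chosen, state how people with no act since viewing are handled.
4. **Other outcomes.** Label them exploratory or apply Holm, leaving out the HIV result.

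**Cost.** Wording and minor programming, with no new data.
- A pooled yes/no primary outcome detects a net change of about 11 to 15 points with 128 pairs, or 12 to 17 with 102. Testing per sex raises this to about 16 to 23 points with 64 pairs, or 17 to 26 with 51. Fewer evaluable last-act pairs are likely, because sexual activity is not an entry criterion.
- Holm's first step over 10 outcomes raises the detectable change from 0.25 to 0.33 SD with 128 pairs (0.28 to 0.37 with 102). The loss is slightly smaller if the HIV result is left out, and the exploratory label avoids it.

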# 26.0 Specimen Use and Banking – N/A

## 27.0 Community-Based Participatory Research – N/A

## 28.0 Sharing of Results with Subjects

28.1 Study results will be shared with participants only through public article publication only if participant contacts researcher about the study, post-study.

#### 29.0 Resources

29.1 I am an associate professor in the college of education. The proposed research consists of cross-sectional qualitative study data. The researcher has previous training in the facilitation of focus groups and extensive training in collecting and analyzing focus group data. The PI has completed a post-doctoral appointment at The Pennsylvania State University's The Methodology Center and learned cutting-edge statistical procedures (quantitative and qualitative) involved in health and prevention research. The PI also currently instructs the research and methodology course within her department program, authors and co-authors manuscripts on sexual risk behavior, and often serves as qualitative (and quantitative) methodologist on student dissertation committees and research papers.

#### 29.2 Resources

There are approximately 50-100 people to come out to various community service events (neighborhood cleanups, cultural fairs, other special events, etc.). With the assistance of a trusted community organization, the Blacklist Association, I anticipate that finding five groups of seven African American adults willing to participate is feasible.

- I intend to devote my academic and summer months to the data collection period and data analysis.
- Facilities include university office, university computer, and department access to schedule a classroom in Farish Hall for research team meetings.

- There is no anticipated medical or psychological resource that subjects might need as a result of a consequence of the human research.
- Any persons assisting with the research data analysis will be adequately informed about this protocol, the research procedures, and their duties and functions. All research team assistants who will potentially participate in either phase of the research will have been personally trained by the PI and are/will be added to the IRB before their human subjects interactions. The student research team member who will have access to the raw data for transcription will be added to the IRB.

# 30.0 Additional Approvals – N/A
